#### **6** INTERVENTIONS

#### **6.1 Interventional treatments**

#### Phase 2 Investigational treatment

Reparixin in oral pharmaceutical form (1200 mg tablets TID), as follows: **GROUP 1:** Reparixin oral tablets 1200 mg TID for 7 days.

- In case of improvement, treatment can be prolonged at discretion of the investigator up to a - maximum of 21 days of treatment in total.

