4.2.3 Safety set

The Safety set (SAF) will consist of all randomized subjects who receive at least one dose of the IMP. SAF population will be analyzed according to the actual treatment received and will be used to present results on safety data.

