6.1 Treatment information

Descriptive analyses of the following parameters will be presented at each available time point:

- For subjects treated with oral reparixin:
 - Total number of oral treatment days
 - Total n° oral tablets administered
- For subjects treated with standard of care:
 - Total number of oral treatment days
- For subjects treated with IV reparixin (if applicable):
 - Total number of IV treatment days

- Total n° IV Vials administered

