6.2 Exposure to IMP

The extent of exposure to IMP in days will be summarized with descriptive statistics by treatment group. The extent of exposure (days) will be calculated using the formula reported in Table 7.

7. Evaluation of Efficacy

As described in section 0, possible modifications in the phase 3 study might be introduced as adaptation from phase 2. In this case, all the impacted below sections will be amended.

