Composite endpoint of phase 2 and Time to event (days) using Oxygen Delivery System Classification	
From ADDITIONAL INFORMATION form:
 
 • if “Has the patient been admitted to the ICU?” = “Yes”, then component1 = “Yes” and date of event1 = Date of Visit • if “Has the patient been admitted to the ICU?” = “No”, then component1 = “No” 
From PATIENT STATUS form:
 
 • if “Is the subject eligible to switch to rescue medication?” = “Yes”, then component2 = “Yes” and date of event2 = Rescue treatment start date 
 ○ If Rescue treatment start date is missing, then Date of Visit will be used • if “Is the subject eligible to switch to rescue medication?” = “No”, then component2 = “No” 
From ADDITIONAL INFORMATION and MECHANICAL VENTILATION forms:
 
 • If “Has the patient been mechanically ventilated?” = “Yes” and type = “Invasive mechanical ventilation”, then component3 = “Yes” and date of event3 = mechanical ventilation start date 
 ○ If mechanical ventilation start date is missing, then Date of Visit will be used • If “Has the patient been mechanically ventilated?” is not empty and type ≠ “Invasive mechanical ventilation”, then component3 = “No” 
From “Worsening based on Oxygen Delivery System Classification” (see above):
 
 • if a patient is classified as “Worsened”, then component4 = “Yes” and date of event4 = Date of Visit • if a patient is classified as not “Worsened” (excluding missing classification), then component4 = “No” 
The composite endpoint is equal to “Yes” if at least one post-baseline component (1-4) is equal to “Yes” and the date of event is the corresponding date of event. In case of more component equal to “Yes”, the first date will be used.
 
Otherwise, if all component (1-4) are equal to “No” the composite endpoint will set as “No”. The date of event will be last date where is known that all components are equal to “No”.
 
Time to composite endpoint (days) = Date of event - Date of randomization

Time from randomization to discontinuation (days)	Time from randomization to discontinuation (days) = Date of study withdrawal – Date of randomization
Extent of exposure (days)	Extent of exposure (days) = Date of last drug administration - Date of first drug administration

Parameter	Derivation

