Time to supplemental oxygen requirement (days)	Time to supplemental oxygen requirement (days) = First Administration start date - Date of randomization
Time to mechanical invasive ventilation use (days)	Time to (invasive) mechanical ventilation use (days) = First (invasive) Mechanical Ventilation start date - Date of randomization
Time to admission to ICU (days)	Time to admission to ICU (days) = Admission date - Date of randomization
Time to rescue medication (days)	Time to rescue medication (days) = First rescue treatment start date - Date of randomization
Overall survival (days)	Overall survival (days) = Date of death - Date of randomization
Subject with improvement based on Likert scale	Improvement = any of these answers: 
 • 1 = minimally better, • 2 = moderately better, and • 3 = markedly better
Cumulative quantity (L) of oxygen treatment	Cumulative quantity of oxygen treatment (L) = Sum of all Quantity (L) in CONCOMITANT OXYGEN TREATMENT form, from randomization to time point of interest. It is defined as supplemental oxygen requirement any increased used of oxygen compared to baseline.
Cumulative duration (hours) of oxygen treatment	Cumulative duration of oxygen treatment (hours) = Sum of duration of oxygen administration (hours) in CONCOMITANT OXYGEN TREATMENT form, from randomization to time point of interest. Duration of oxygen administration (hours) = Administration end date/time - Administration start date/time / 60
Cumulative duration (hours) of mechanical ventilation	Cumulative duration of mechanical ventilation (hours) = Sum of duration of mechanical ventilation (hours) in MECHANICAL VENTILATION form, from randomization to time point of interest. Duration of mechanical ventilation (hours) = End date/time - Start date/time / 60
Duration (days) of ICU stay	Duration of ICU stay (days) = Discharge date - Admission date
Change from baseline	For changes from baseline the baseline value will constitute the minuend and the later value the subtrahend.
Conversion of Time Intervals	If a time interval was calculated in minutes, hours or days and needs to be converted into months or years the following conversion factors will be used: 
 • 1 hour = 60 minutes • 1 day = 24 hours • 1 week = 7 days • 1 month = 30.4375 days • 1 year = 365.25 days

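### SAP Table 7 computes extent of exposure as last minus first dosing date with no plus one, so a patient dosed on a single date shows 0 days and dosing on days 1 to 7 shows 6

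*SAP*

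**What the plan says.** SAP section 9.1, Table 7, gives the derivation: "Extent of exposure (days) = Date of last drug administration - Date of first drug administration". SAP section 6.2 relies on it: "The extent of exposure (days) will be calculated using the formula reported in Table 7". That section summarises the result descriptively by treatment group, and SAP Table 3 assigns the summary to the Safety set. Entry to that set needs only one dose: "The Safety set (SAF) will consist of all randomized subjects who receive at least one dose of the IMP".

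Protocol section 6.1 states treatment length in days: "Reparixin oral tablets 1200 mg TID for 7 days", which may be extended to a "maximum of 21 days of treatment in total".

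SAP section 6.1 separately lists "Total number of oral treatment days" and a tablet count. Table 7 has no row that derives the treatment-day count.

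**The concern.** Both the first and the last dosing date are days on which the patient took drug. A plain subtraction of dates drops one of them. The protocol describes the course in days of treatment, so a reader will compare the exposure table with 7 and 21. A patient who took every dose on calendar days 1 to 7 would appear as 6 days and look slightly under-treated.

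The single-date case is worse. The patient is in the Safety set because drug was taken, yet the table shows no exposure. The plan foresees very short courses: protocol section 8.2 provides for replacing patients in the active group who are withdrawn before 24 hours of treatment. Some of them may have all their doses on one date.

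What is at stake is the accuracy of a descriptive safety table and its agreement with the neighbouring treatment table.

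**Working it through.** The documents give no numerical exposure result, so there is no figure to reproduce. The check is calendar arithmetic on the stated rule.

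**Inputs**
- Rule: last dosing date minus first dosing date (SAP Table 7).
- Core course 7 days, three doses a day; maximum 21 days (protocol section 6.1).
- Population: at least one dose (SAP section 4.2.3).

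**Formulas.** For dosing on calendar days 1 to k:
- Table 7 gives k − 1.
- The inclusive count of dates is k − 1 + 1 = k.
- The relative shortfall is 1/k.

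| Dosing dates | Table 7 | Inclusive count | Shortfall |
|---|---|---|---|
| Day 1 only | 0 | 1 | 100% |
| Days 1–2 | 1 | 2 | 50% |
| Days 1–7 | 6 | 7 | 14.3% |
| Days 1–14 | 13 | 14 | 7.1% |
| Days 1–21 | 20 | 21 | 4.8% |

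**Could it be meant as clock time?** Where the SAP uses clock time it says so. The oxygen duration row in Table 7 reads "Administration end date/time - Administration start date/time / 60". The exposure row names dates only and is expressed in days.

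**Late start on day 1.** The core course is 7 × 3 = 21 doses.
- Three doses on the first date leave 18, which need 6 further dates: 7 dates in all, and Table 7 gives 6.
- Two doses on the first date leave 19, and one dose leaves 20. Either needs 7 further dates: 8 dates in all, and Table 7 gives 7.

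In the late-start case the rule returns the nominal course length, although it is still one below the number of calendar dates.

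**Is it corrected elsewhere?** No plus one, inclusive-counting rule or clock-time adjustment for exposure appears in the protocol or the SAP.

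**The case against.** The best defence is that Table 7 uses plain date differences throughout, including time from randomization and length of ICU stay, so the row may be a consistent elapsed-time convention with a poor label. With doses 8 hours apart, 21 doses span 20 × 8 = 160 hours, or 6.7 days, so neither 6 nor 7 is far off. If dosing runs into an eighth date, the present rule returns 7 and a plus one would return 8 for a nominal 7-day course. Adding 1 also gives a calendar span, not a count of dosed days, and SAP section 8.1 tabulates temporary interruptions (although protocol section 8.2 does not allow them). Finally, SAP section 6.1 already reports treatment days and tablets, so a one-day patient's dosing would be visible there.

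Most of this limits the consequence; it does not rescue the rule. An elapsed-time reading is not stated, and it still prints 0 days for a treated patient. The points about the eighth date and interruptions do stand, and the fix has to state them.

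A reader might infer more than the documents support:

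- *Adverse event rates would be overstated.* SAP section 8.1 plans counts of subjects and events. None uses exposure time as a denominator.
- *Phase 3 treatment duration rests on this figure.* The protocol leaves that duration to phase 2 results in general and does not name the exposure summary. Neither exposure nor duration is listed in SAP Table 6.
- *The report will show 7 in one table and 6 in the next.* This is conditional, because SAP section 6.1 gives no derivation for treatment days.
- *With 32 reparixin patients, 32 of 32 × 7 = 224 patient-days are lost (14%).* This holds only if every course falls on exactly seven calendar dates. The documents give no first-dose times.

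**Conclusion.** The point holds as a definite but small derivation error. As written, Table 7 returns one day fewer than the number of calendar dates from first to last dose: 0 for a single date, 6 for days 1 to 7, 20 for days 1 to 21. The shift is always downward against calendar dates and proportionally largest for the shortest courses. The one plainly wrong display is zero exposure for a patient who is in the Safety set because of having been dosed.

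The effect stays within the descriptive exposure table. It does not reach the primary endpoint, power, type I error or any planned adverse event table. A one-day mismatch with the treatment days in SAP section 6.1 is possible, but only if those are counted inclusively.

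The conclusion assumes that exposure in days is meant to be read as calendar days from first to last dose inclusive, which is the natural reading given that the protocol states treatment length in days.

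**What to change.** Three changes, all in the SAP:

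1. In Table 7, append + 1 to the exposure row, so that it is last dosing date minus first dosing date plus 1.
2. Add a note that this is the calendar span from first to last dose, including any interruption, and that a course whose doses run into an eighth date will show 8.
3. Give a derivation for the treatment-day count in SAP section 6.1, and reconcile the exposure figure with that count and the tablet count.

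The population and grouping in section 6.2 can stay as they are. The cost is one line in the table, a short note, one further derivation and the matching program edits. Trial conduct and inference are unaffected. The one drawback is that some nominal 7-day courses will show as 8, which the note explains.

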3.2 Sample size justification

The sample size of the full phase 2/3 study is calculated based on data from clinical experience and on Sponsor expectations as reported in Table 2:

Table 2: Assumptions for primary endpoints

Primary endpoint*	Standard of care (control)	Reparixin
Time to primary endpoint of phase 2	2 days	5 days
Time to primary endpoint of phase 3	2-4 days	4-8 days

* see section 3.5.1.

Based on the following assumptions:

- an enrollment phase of 2 months,

- a total follow-up of 21 days,
- a randomization ratio (reparixin:control) of 2:1
- an exponential distribution for survival probability $S(t) = e^{-\lambda t}$,
- a comparison between treatment by means of a log-rank test,
- an interim analysis framework as described in section 4.5, and
- a correction of the type I and II errors by means of O'Brien-Fleming spending functions

a total of 109 events (corresponding to approximately 111 subjects) will allow to provide >80% power to show superiority of reparixin vs standard of care in terms of primary endpoint of phase 3, controlling the type I error under 0.025.

Based on the same assumptions reported above, phase 2 portion of the study will be performed when a total of 46 events (corresponding to approximately 48 subjects) has happened. This allow to achieve approximately 80% power to show superiority of reparixin vs standard of care in terms of (not severe) primary endpoint of phase 2, controlling the type I error under 0.025.

The remaining portion of the 111 patients will be enrolled in the phase 3 study segment. Anyhow, due to the novel nature of the COVID-19 pandemic and being the primary efficacy endpoint planned in phase 3 not well established, it may require confirmation based on phase 2 data. For this reason, at the end of the phase 2 portion, power calculations may be reassessed, and sample size may be re-estimated for phase 3.

The adaptive design allows for the assessment of efficacy endpoint in phase 2 which are then seamlessly confirmed in the phase 3. Since primary endpoint of phase 3 will be tested only if superiority of reparixin is shown in phase 2 (at interim or final stage), the overall type I error of the study will be controlled at 0.025 via the hierarchical testing procedure.

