4.2.4 Full Analysis set

The Full Analysis Set (FAS) will consist of all randomized subjects who receive at least one dose of the IMP. FAS population will be analyzed according to ITT principle, i.e. by treatment allocation regardless happening of intercurrent events. The FAS population will be used for the primary analyses of the study and to present results on efficacy data.

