4.8 Handling of missing and incomplete data

The number of subjects with missing data will be presented under the "Missing" category, if present. Missing values will not be included in the denominator count when computing percentages. Similarly, only the non-missing values will be evaluated for computing summary statistics for continuous endpoint. Any exception will be clarified as a note.

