7.2.2 Comparison between treatments

Along with the above summary statistics, comparisons between treatments will be performed as detailed in the next sub-sections. Parametric test (i.e. two-sample t-test for continuous variables, Chi-square test for categorical) will be adopted as first choice. In case the required assumptions are not met, the corresponding non-parametric counterpart will be used (i.e. the two-sample Mann–Whitney U test for continuous variables, and the Fisher’s Exact test for the categorical). Normality of continuous data is assessed by Kolmogorov-Smirnov test.

Comparison will be performed at each available time point, where applicable. Any exception will be declared.

7.2.2.1 *Composite endpoint of phase 2 using Oxygen Delivery System Classification*

The composite endpoints will be summarized along with their single component by a binomial response rate at each time point (only the first event will be considered). The Clopper-Pearson method will be used to estimate the two-sided 95% CIs.

Time to composite endpoint(s) will be performed using the KM methodology and the one-sided log-rank test will be used to test for differences between treatment groups.

7.2.2.2 *Changes in clinical severity score*

Number and proportion along with the 95% confidence interval (Clopper-Pearson’s formula) of subjects with a clinical severity score improvement of at least two points compared to randomization or live discharge from the hospital will be calculated and compared.

7.2.2.3 *Dyspnea severity (Liker scale and VAS scale)*

The comparison of the Liker scale between the two study treatment arms will be performed by means of Wilcoxon signed-rank test, given its ordinal nature.

Number and proportion along with the 95% confidence interval (Clopper-Pearson’s formula) of subjects with

any improvement (improved vs not-improved) will be calculated and compared.

VAS scale comparison between treatments will be performed according to its continuous nature.

7.2.2.4 *Changes in body temperature*

Comparison between treatments in change from baseline of the body temperature will be performed according to the continuous nature of the variable.

7.2.2.5 *Incidence of supplemental oxygen treatment*

Number and proportion along with the 95% confidence interval (Clopper-Pearson's formula) of subjects who worsened according to PaO₂/FiO₂ and to Oxygen Delivery System Classification based on oxygen support will be calculated and compared.

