At each time point the number and proportion of patients within each class (Severe, Moderate, or Mild for PaO₂/FiO₂; Invasive, High Flow, or Low Flow for the type of support) will be provided.

Finally, summary of cumulative quantity (L) and cumulative duration (hours) of oxygen treatment will be performed at 7 days and subsequent time points considering the variable as continuous.

7.2.2.6 *Incidence and duration of mechanical ventilation use*

Number and proportion along with the 95% confidence interval (Clopper-Pearson's formula) of subjects requiring mechanical ventilation will be calculated and compared.

Comparison between treatments in cumulative duration (hours) of mechanical ventilation will be performed at 7 days and subsequent time points considering the variable as continuous. Analysis will be performed overall and stratified by Invasive/Non-invasive mechanical ventilation.

7.2.2.7 *Incidence of ICU admission need*

Number and proportion along with the 95% confidence interval (Clopper-Pearson's formula) of subjects requiring ICU admission will be calculated and compared.

Comparison between treatments in duration (days) of ICU stay will be performed considering the variable as continuous.

7.2.2.8 *Change from baseline in lung damage extension and lung exudation degree (assessed by Chest CT or Rx)*

The comparison of the clinical evaluation of lung damage extension and lung exudation between the two study treatment arms will be performed by means of Wilcoxon signed-rank test.

7.2.2.9 *Respiratory parameters*

Change from baseline of FiO₂, Respiration rate, PaO₂, SpO₂ and PaO₂/FiO₂ will be compared between treatments considering the continuous nature of these variables.

7.2.2.10 *CRP and Hs-CRP*

CRP (mg/L) and Hs-CRP (mg/L) will be compared between treatments considering their continuous nature.

7.3 **Analysis of exploratory efficacy endpoints**

Explorative endpoints (section 3.5.3) will be analyzed at each available time points by means of descriptive statistics. Specifically, analyses will be provided for baseline visit, each post-baseline visit, and the change from baseline measurements to each visit. Comparison between treatments will be performed by means of two-sample t-test or, if assumptions of normality is not confirmed (by Kolmogorov-Smirnov test), two-sample Mann-Whitney U test.

In case of different units of measure considered for the same laboratory parameter, all values will be converted

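### The between-arm comparison of ICU stay covers only patients who entered and left ICU, so it is not a randomized comparison and its direction depends on which stays the drug averts

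*SAP*

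**What the plan says.** Table 7 in SAP 9.1 gives the whole derivation: "Duration of ICU stay (days) = Discharge date - Admission date". SAP 7.2.2.7 then orders the test: "Comparison between treatments in duration (days) of ICU stay will be performed considering the variable as continuous". Under SAP 7.2.2 the first choice is the "two-sample t-test for continuous variables, Chi-square test for categorical", with Mann–Whitney as the fallback for continuous data. For missing data, SAP 4.8 says that "only the non-missing values will be evaluated for computing summary statistics for continuous endpoint".

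Three neighbouring rules matter:

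- SAP 4.2.4 sets the population for efficacy: "The FAS population will be used for the primary analyses of the study and to present results on efficacy data", analysed by allocated arm.
- SAP 7.2.2.7 also has an incidence analysis: the number and proportion "of subjects requiring ICU admission will be calculated and compared".
- Table 7 treats ventilation time differently, as "Sum of duration of mechanical ventilation (hours) in MECHANICAL VENTILATION form, from randomization to time point of interest". Oxygen time follows the same pattern.

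No section gives never-admitted patients 0 days, closes a stay still open at last contact, sums readmissions, or says how a death in ICU enters the duration. The censoring rules in SAP 4.1 and the Table 7 entry on the last available date serve time-to-event variables, not this one.

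**The concern.** A never-admitted patient has neither date, and a patient still in ICU has no discharge date. Neither can enter a t-test or a rank test on this variable. What remains is patients who were admitted to ICU and left it. ICU admission is a component of both primary composites (SAP 3.5.1), so membership of that subset is itself an outcome the drug is intended to change. Randomization does not balance it, even with no deaths and no data lost.

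At stake is the reading of the ICU results. A drug that spares patients ICU time can show a longer stay, no difference or a shorter stay, depending on which admissions it prevents. By the same logic, a drug that adds short admissions could look favourable.

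**Working it through.** **The plan's own figure.** There is none. The documents state no ICU admission rate, stay length or expected difference. The inputs below are assumptions, apart from the arm sizes: 48 patients at "a randomization ratio (reparixin:control) of 2:1" gives 32 and 16.

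**Formulas.**
- SAP variable = total ICU days among admitted and discharged patients ÷ number of such patients.
- All-patient variable = total ICU days ÷ number randomized, with 0 for the never admitted.

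**Worked example at phase 2 size** (assumed: half would be admitted, half of those for 4 days and half for 14; reparixin averts every short stay; no deaths, no open stays).
- Control: 4 stays of 4 days and 4 of 14 days, total 72 days. SAP variable 72/8 = 9.0; per randomized patient 72/16 = 4.5.
- Reparixin: 8 stays of 14 days, total 112 days. SAP variable 112/8 = 14.0; per randomized patient 112/32 = 3.5.
- The SAP variable reads 5.0 days worse on reparixin. ICU days per patient are 1.0/4.5 = 22% lower.

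**Dependence on which stays are averted** (assumed: 40% control admission, half of stays 3 days and half 15 days). Control is 9.0 days on the SAP variable and 0.4 × 9.0 = 3.6 per patient. For reparixin:

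| Averted | SAP variable | Per randomized patient |
|---|---|---|
| Half of short stays | (0.1×3 + 0.2×15)/0.3 = 11.0 | 3.3 |
| Half of all stays | (0.1×3 + 0.1×15)/0.2 = 9.0 | 1.8 |
| Half of long stays | (0.2×3 + 0.1×15)/0.3 = 7.0 | 2.1 |

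ICU days per patient fall in all three rows. The SAP variable rises, stays level and falls.

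**Range when only short stays are averted** (20–60% admission, 25–100% of short stays averted, stays of 3/15 or 5/12 days). The SAP variable shifts by +0.5 to +6.0 days while all-patient days change by −0.07 to −1.5. The signs are opposite throughout.

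**Open stays dropped as well** (simulated: 40% admission, admission day uniform on 1–10, short mean 4 days, long mean 15 or 20, cut-off day 28 or 31). Differences are reparixin minus control:

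| Averted | SAP variable | All-patient days |
|---|---|---|
| Half of short stays | +1.5 to +2.0 | −0.4 |
| All short stays | +4.7 to +6.6 | −0.8 |
| Half of all stays | 0.0 | −1.8 to −2.2 |
| Half of long stays | −1.4 to −1.7 | −1.4 to −1.8 |

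In the first row, stays still open are 5–17% of control and 7–23% of reparixin admissions.

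**How often the test itself misleads in phase 2** (simulated: 32 vs 16 patients, 40% control admission, log-normal stay with median 7 days and log-SD 0.6–1.0, admission day 1–10; reparixin averts 60% of stays under 7 days and 10% of longer ones). The mean difference is +1.3 to +1.8 days and points against reparixin in about 71% of trials. The test is significant against reparixin at 0.05 in only 7–8% of trials (t-test) or about 7% (Mann–Whitney), with roughly 7–8 reparixin and 6 control patients contributing. Averting 35% of both kinds gives about 0; the reverse pattern gives −1.3 to −1.6 days.

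**The case against.** The strongest reply is that little rests on this variable. ICU duration is not a listed endpoint: SAP 3.5.2 and Protocol section 3 list only the incidence of ICU admission. That incidence is compared in the same subsection, and time to first ICU admission is analysed in SAP 7.1.3. In the example, a reader would see 8/16 against 8/32 admitted beside the 9.0 and 14.0 days. SAP 7.1.3.1 bases the decision to go to phase 3 on the primary analysis alone. All of this stands and limits the weight of the point. It does not make the duration test a randomized comparison.

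It is also fair that the exclusion is inferred. SAP 4.8 speaks of summary statistics, a never-admitted patient may be regarded as not applicable rather than missing, and the CRF is not among the documents. But a test cannot use a blank, and the SAP supplies no value to fill it.

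A reader might infer that averted admissions will show up as a longer stay on reparixin, or that the plan is likely to produce a significant false signal of harm. The documents do not support either. Nothing in them says that reparixin would avert mainly short stays, and the other patterns give no difference or a shorter stay. Even in the unfavourable scenario, a significant wrong-way test is uncommon.

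Finally, simply counting ICU days with 0 for the never admitted would be unsafe. A death on the ward would score 0 days, the best value, and a death on the second ICU day only 2. A replacement needs a death rule.

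**Conclusion.** The point holds as a flaw in a supportive analysis. Followed exactly, SAP 9.1 and 7.2.2.7 compare a subset chosen by a post-randomization outcome, although the SAP assigns efficacy results to the FAS. The direction of the distortion is not fixed: 9.0 against 14.0 days in the example where short stays are averted, about zero when stays are averted evenly, and a shorter stay when long ones are averted. These sizes rest on assumed ICU rates and stay lengths and on no deaths.

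In phase 2, 20–60% control admission would leave about 3–10 control patients (16 × 0.2 to 16 × 0.6) and 5–14 reparixin patients (32 × 0.2 × 0.75 to 32 × 0.6 × 0.75, half of short stays averted) before open stays are dropped. An uninformative or wrong-signed estimate is the likely result. The primary tests and the phase 3 decision are not affected.

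**What to change.** In Table 7 and SAP 7.2.2.7, replace the between-arm comparison of ICU stay with days alive and out of ICU from randomization to one fixed day within follow-up, in all FAS patients. Day 21 is a natural choice because SAP 3.2 assumes that follow-up. State these rules:

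- Never-admitted patients alive at day 21 score the full 21 days.
- An ICU stay still open counts as ICU days up to day 21.
- Readmissions are summed where their dates are recorded.
- Death by day 21 scores 0, the worst value.
- A rule is given for withdrawal before day 21.

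If every stay in the worked example falls within the 21 days and nobody dies, the new variable averages 21 − 4.5 = 16.5 days on control and 21 − 3.5 = 17.5 on reparixin, which has the right sign. Compare arms with a rank test or a bootstrap interval for the mean. Keep ICU stay among the admitted as description only, without a test.

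The cost is one derivation rule and one revised paragraph. Table 7 already presupposes admission and discharge dates. Whether the CRF captures readmission dates must be checked, since the schedule of evaluations lists ICU admission only as yes or no. The downside is a skewed variable with many tied values that partly repeats the incidence comparison.
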